## Data & Safety Monitoring

Summarize safety concerns, and describe the methods to monitor research subjects and their data to ensure their safety, including who will monitor the data, and the frequency of such monitoring. If a data monitoring committee will be used, describe its operation, including stopping rules and frequency of review, and if it is independent of the sponsor (per 45 CFR 46.111(a) (6)).

## Safety Monitoring

Although blood pressure will be monitored by research staff during the study, blood pressure management will continue to be up to participants' health care providers (HCPs). Patients who exhibit screening "office" averaged BP greater than 160/100 mm Hg across the two screening sessions will not be eligible to participate in the study and will be provided their screening BPs with the recommendation that they provide this information to their HCP within 72 hours. For participants already enrolled in the study, if "office" averaged BP values exceed 160/100 mm Hg, the participant will be provided those BP readings at that time, and will be encouraged to share the results with their HCP within 72 hours; with patient written consent, we also will provide the BP readings to their HCP. All eligible participants will have completed the CBT-I intervention within approximately 3 months from study enrollment. Both pre- and post-treatment ambulatory blood pressure records and study-assessed "office" blood pressures will be provided to participants at that time (i.e., after ~12 weeks), and with their consent (using a Redcap electronic medical authorization or paper authorization form), also will be provided to their HCP for follow-up as needed. In the event that participants do not have a HCP, a list of local family HCPs who are accepting new patients will be provided to them.

Participants will undergo follow-up assessments 6 months after the CBT-I intervention. Any intervening treatments including antihypertensive medications, will be documented. It should be emphasized that participants will not be prohibited from initiating pharmacologic treatment for high blood pressure at any time during the study. At all assessment phases, participants' medications will be documented. Upon completion of their participation in the study (approximately 9 months after initial screening assessments confirmed their eligibility), for participants who exhibit no improvement in their insomnia symptoms, we will refer them back to their HCP for consideration of alternative approaches to treating their insomnia.

Potential participants suspected by questionnaire and diagnostic sleep interview to have obstructive sleep apnea will also have an overnight sleep apnea screening assessment using the WatchPAT One (Itamar Medical) system. Moderate to severe sleep apnea is an exclusion criterion, as defined by an apnea-hypopnea index (AHI) >15. Potential participants excluded due to an elevated AHI will be provided a letter indicating their AHI and invited to share this information, indicating suspected sleep apnea, with their HCP.

Although we are not selecting, or excluding, hypertensive patients based upon their level of distress or depression, our assessments may determine the presence of severe depression. If patients are acutely

suicidal, they will be evaluated by our licensed study clinical psychologist ([name]); appropriate referral or admission procedures will be initiated, and they will be dropped from further study. Specifically, should participants become acutely suicidal [if they endorse a response of 2 or 3 on item 9 (suicide item) on the BDI-II at the end of the 6-week run-in or after the 6-week CBT-I treatment program] they will be evaluated by our study psychologist within 24 hours and will be referred for treatment as needed.

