**ReScreening** - If a participant fails to meet all eligibility criteria, but remains interested in participating in the study, they will have the option to be rescreened at a future date. If the rescreening occurs within 3 months, only the eligibility criterion which made them ineligible initially will be reassessed in order to ascertain their eligibility at rescreening; if rescreening occurs after more than 3 months, then the full screening protocol will be repeated. The participant will be re-consented at the time of rescreening.

**Office BP Screening Assessment.** At the first lab screening session, BP will be determined by unattended automated office blood pressure (AOBP) measurement using the Omron HEM-907 Professional Intellisense BP Monitor. AOBP measurement minimizes the “white coat” effect and correlates more closely with ambulatory BP than do standard office measurement techniques. After seating the individual in a quiet room, a cuff of appropriate size will be wrapped around the individual’s non-dominant upper-arm and the Omron HEM-907 will be operated in automated mode: After starting the

monitor, the Research Assistant will leave the room, and after a lapsed time of 5 minutes, the monitor will take a total of three BP measurements, each 2 minutes apart; the average of these three readings will be used to define office BP at that visit. If BP meets the studies inclusion/exclusion criteria, a second screening session will be scheduled, and if BP continues to meet criteria, the individual will be enrolled as a study participant (assuming all other inclusion/exclusion criteria are also met). This method for office BP assessment also will be completed subsequently at all four laboratory assessment sessions.

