## Selection of Subjects

**Inclusion Criteria.** Systolic BP  $\geq$  130 mm Hg based upon two standardized BP screening assessments a current diagnosis of insomnia disorder as defined in the International Classification of Sleep Disorders (ICSD-3);84 or undiagnosed, but suspected, insomnia disorder that is confirmed at their screening lab visit; an age range of 30-60 years.

**Exclusion Criteria.** Uncontrolled hypertension (screening office BP > 160/100 mm Hg); antihypertensive medication use; cardiovascular medications; previously diagnosed moderate or severe obstructive sleep apnea; severe obesity defined by BMI > 40 kg/m^2; pacemakers; atrial fibrillation; acute coronary syndrome or coronary revascularization procedure within 6 months of enrollment; congestive heart failure; identifiable cause of hypertension (e.g., primary hyperaldosteronism, renal artery stenosis, untreated hyper- or hypothyroidism, chronic kidney disease, Cushing's disease, pheochromocytoma, coarctation of the aorta); severe uncorrected valvular heart disease; current pregnancy; active diagnosis of psychosis, bipolar disorder, current treatment of PTSD with exposure based therapy; severely impaired hearing or speech; participation in another interventional study to address insomnia; rotating shift workers; diabetes; prominent suicidal or homicidal ideation (as assessed through a clinical interview); psychiatric hospitalization within the past 12 months; unstable comorbid sleep disorder requiring assessment and/or treatment outside of the study protocol; medical or psychiatric conditions judged to be the primary cause of insomnia; alcohol or drug abuse within 12 months; dementia; inability to comply with the assessment procedures or inability to provide informed consent.

**Identification.** The study coordinator and research associate will identify patients using the electronic medical records (Maestro). A detailed description is below in Subject Recruitment. If a participant is interested and their electronic medical record (EMR) is not available, study staff can ask the participant the eligibility criteria that would have been collected in the EMR to collect the medical history necessary to determine eligibility.

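### The upper screening BP limit is applied at each session in one section and to a two-session average in another, and the 72-hour advice, as written, misses people stopped at session 1

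*Combined protocol and SAP*

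**What the plan says.** Four places in the combined protocol and SAP bear on this.

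- **Design & Procedures, Office BP Screening Assessment.** Each visit yields one office BP from three automated readings: "the average of these three readings will be used to define office BP at that visit". What follows session 1 depends on that value: "If BP meets the studies inclusion/exclusion criteria, a second screening session will be scheduled". Session 2 has to pass the same test before enrolment, other criteria permitting. The test covers inclusion and exclusion criteria, so it takes in both the lower and the upper BP limit.
- **Selection of Subjects.** The lower limit (systolic BP of at least 130 mm Hg) is "based upon two standardized BP screening assessments". The upper limit excludes a screening office BP above 160/100 mm Hg. Neither entry says whether the value is per session or averaged.
- **Safety Monitoring.** Candidates with "averaged BP greater than 160/100 mm Hg across the two screening sessions will not be eligible". The same people "will be provided their screening BPs with the recommendation that they provide this information to their HCP within 72 hours".
- **Risk/Benefit Assessment.** A general line says patients will be referred to local physicians when needed. It gives no BP threshold, no timing and no handover of readings.

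For participants already enrolled, Safety Monitoring triggers its BP notification on office averaged values above 160/100 mm Hg, with no two-session condition.

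**The concern.** Two things are at stake.

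The first is eligibility. A candidate whose two sessions fall on opposite sides of the upper limit can be in or out depending on which section staff follow. The trial report could not then state one BP entry rule.

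The second matters more and needs no assumption about BP spread. The advice to take high readings to a health care provider is attached to a value that needs two sessions. The screening procedure books no second session for someone already above the limit at the first. Followed as written, the two sections leave that person outside the specific protection, however high the first reading.

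**Working it through.** **Step 1: the rules side by side.** Write S1 and S2 for office BP at the two sessions, each the mean of three readings.

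- Session rule (Office BP Screening Assessment): S1 and S2 must each be at or below 160/100.
- Averaged rule (Safety Monitoring): (S1 + S2)/2 must be at or below 160/100.

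If both sessions are at or below the limit, so is their mean. The rules therefore disagree in one direction only: the average admits people whom the session rule rejects.

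**Step 2: an example.** Take the limit as exceeded when either component is above it, which the documents do not spell out. A candidate has 164/96 and then 152/90. The means are (164 + 152)/2 = 158 and (96 + 90)/2 = 93. The session rule stops this person at session 1, because 164 > 160. The averaged rule does not exclude, because 158/93 is within the limit.

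**Step 3: can the advice be reached?** S1 above the limit means the criteria are not met, so no session 2 is booked, no S2 exists and there is no two-session average. The Safety Monitoring trigger is then undefined. Under the session rule only a person who passes session 1 can reach it.

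**Step 4: illustrative size.** The documents state no figure, so there is none to reproduce, and they give no screening BP distribution. All inputs here are assumptions, systolic only: true SBP T ~ N(m, s), session value Sj = T + Ej, and independent Ej ~ N(0, e). The lower limit is applied at each session under both rules, so only the upper limit differs.

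- Session rule: 130 ≤ S1 ≤ 160 and 130 ≤ S2 ≤ 160.
- Averaged rule: S1 ≥ 130, S2 ≥ 130 and (S1 + S2)/2 ≤ 160.

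Two million simulated candidates per row:

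| m, s, e (mm Hg) | Rules disagree, % of candidates | Rules disagree, % of those eligible on averaged rule | Of mean > 160, % with S1 > 160 |
|---|---|---|---|
| 138, 12, 6 | 3.4 | 5.6 | 79.8 |
| 138, 12, 8 | 5.2 | 9.3 | 77.2 |
| 138, 12, 10 | 6.9 | 13.6 | 74.5 |
| 140, 15, 6 | 4.7 | 8.3 | 84.7 |
| 140, 15, 8 | 6.5 | 12.5 | 81.6 |
| 140, 15, 10 | 8.3 | 17.0 | 79.3 |

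Check on the first row: the two-session mean has SD √(12² + 6²/2) = 12.73, so P(mean > 160) = 1 − Φ(22/12.73) = 1 − Φ(1.73) = 0.042, which matches the simulated 0.042.

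**Step 5: wider inputs.** With m from 135 to 150, s of 10 or 15, and e from 5 to 10, disagreement runs from about 1% to 15% of candidates (2% to 23% of those eligible on the averaged rule). The last column runs from about 71% to 90%.

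**The case against.** The best reply is that the conflict may be loose drafting. Office BP is already an average of three readings, and the next sentence of Safety Monitoring uses averaged for enrolled participants, where a single visit's mean fits. The screening sentence could then mean visit averages above the limit at the screening sessions. That reading softens the eligibility conflict. It does not close the advice gap, because the sentence still refers to both sessions and a person stopped at the first has only one.

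A second reply is that staff would hardly withhold a high reading, and Risk/Benefit Assessment provides for referral when needed. That is fair as far as it goes: the gap concerns the specific 72-hour advice, not all referral. But the general line fixes no threshold, timing or handover of readings, so it does not replace that advice.

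A third reply is that no harm to the analysis is shown. This stands. All participants receive the same intervention, and the Aim 1 model adjusts for baseline mean 24-hour BP and pretreatment dipping.

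Three stronger readings are tempting and not supported.

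- **That the 130 mm Hg limit is contradicted too.** No section averages it. The wording in Selection of Subjects is ambiguous and compatible with the session rule. A pair such as 137 then 127 (mean 132) shows the ambiguity, not a conflict.
- **That 19–34% of eligible candidates are affected.** Under the Step 4 inputs this range appears only if both limits are averaged, which no section says.
- **That two sites would enrol different BP populations.** Subject Recruitment and Compensation adds the second institution as a recruitment site. It does not say that BP is measured or eligibility decided there.

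**Conclusion.** The point holds in a narrow form. Read literally, the screening procedure and Safety Monitoring apply the upper BP limit to different quantities, and Selection of Subjects does not decide between them. As written, the 72-hour advice does not cover a person stopped for high BP at session 1. That second conclusion follows from the text alone.

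The sizes are illustrative. Under normal systolic values with the Step 4 inputs, the two upper-limit rules disagree for about 3–8% of candidates, or 6–17% of those eligible on the averaged rule. About 75–85% of people whose two-session mean would exceed 160 would already be out at session 1. The first range depends heavily on the assumed spread and falls to about 1% of candidates in some settings, so it does not support saying that eligibility changes for many. The second stays above 70% throughout the wider range. Diastolic BP is not modelled.

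The protocol should be corrected on this point, for consistent eligibility and participant safety; no bias in the primary analysis is claimed. Which BP rule is clinically right is not judged here.

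**What to change.** Reconcile the Office BP Screening Assessment text, Selection of Subjects and Safety Monitoring:

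1. Name one decision unit for the upper limit (each session, or the mean of two) and use it in all three places.
2. In the same edit, state the unit for the 130 mm Hg lower limit.
3. Reconcile the Safety Monitoring notification with the screening sequence, so that it states whether it covers people stopped at session 1.

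The sponsor's medical lead decides the clinical rule and its wording. The cost is a protocol wording change, with no added visits or measurements.

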#### C.6. QUALITY OF LIFE (QOL) ASSESSMENTS

CBT-I has been shown to result in marked improvements in QoL in medical patient populations where insomnia is commonly comorbid. In the present proposal, we will explore QoL changes that may accompany improved sleep quality following the CBT-I intervention. We will also explore QoL and psychosocial distress as potential moderators of the changes in CVD risk mechanisms accompanying sleep quality changes. A demographic information will be complete once and will be used to assess ethnicity, smoking, and alcohol use and menopausal status where applicable. The following assessments will be made at baseline, post-6-week run-in, post-CBT-I intervention, and at 6-month follow-up.

Health-Related Quality of Life will be measured using the Short Form-36 Health Survey (SF-36), which provides a physical health and mental health QoL summary score.

**Depressive Symptoms.** The Beck Depression Inventory II (BDI-II) will be used to assess depressive symptoms. It is a widely used self-report measure of depressive symptoms, consisting of 21 items, each corresponding to a specific category of symptoms and attitudes. The inventory has been studied extensively since it was first developed in 1961. It has been shown to be both a reliable and valid measure of the severity of depressive symptoms. In cardiac populations, depressive symptoms assessed using the BDI and the revised BDI-II, as well as changes in BDI over time, have been related to clinical outcomes. It should be emphasized that the BDI-II is not a diagnostic instrument, but rather a method for determining the presence and severity of depressive symptoms.

**Anxiety Symptoms.** Anxiety will be measured using the state and trait anxiety versions of the State-Trait Anxiety Inventory (STAI). The STAI consists of two separate 20-item self-report inventories, one measuring state anxiety and the other trait anxiety. The STAI has been shown to be associated prospectively with increased CVD risk and all-cause mortality.

Perceived Stress will be measured by the Perceived Stress Scale (PSS). The PSS consists of 10 items that are evaluated on a 5-point Likert scale.

Daytime Sleepiness will be assessed by the Epworth Sleepiness Scale (ESS), an 8-item measure of perceived daytime sleepiness.

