The risk of serious injury due to study participation is negligible. All measurement techniques have been used extensively by the investigative team without a single adverse event. Procedures for protecting subjects against potential risks include screening procedures. Patients will be referred to their local physicians when needed. We also will take special precautions to ensure the safety of patients with clinically significant depression, i.e., patients with BDI-II scores  $>29$  (moderate-severe depression) or who are actively suicidal. Although we are not pre-selecting patients with hypertension and comorbid insomnia based upon their level of distress or depressive symptoms, our assessments may determine the presence of significant clinical depression. In the unlikely event that patients are determined to be actively suicidal, they will be queried for suicidal plans, intent and past suicidal behaviors. Those with current active suicidal ideation, history of suicidal acts within the past 12 months, or bipolar disorder or psychosis will not be enrolled in the study and appropriate referral or admission procedures will be initiated. If a patient exhibits moderate-severe depression (e.g., BDI-II  $>29$ ) at baseline, we will inform the participant and, with his or her permission, notify their primary care physician. Any participant who is determined to be actively suicidal over the course of the study will be referred for psychiatric evaluation and possible hospital admission. If they are found to be at immediate risk, emergency procedures will be followed including requesting an ambulance to take the patient to the emergency department (ED) for immediate evaluation and treatment. Patients who score  $>29$  on the BDI-II and are not actively suicidal will be informed about the results of our assessment, and with their consent, we will inform their physicians for further evaluation and possible treatment. In this manner, we believe that risk will be minimized. Any enrolled patient who becomes actively suicidal (i.e., who scores  $>1$  on item 9 of BDI-II) will be immediately evaluated by our study psychologist for suicidal plans and intent. If a patient is considered acutely suicidal, he or she will be dropped from further participation and will be referred for either urgent evaluation by a psychiatrist or prompt ED evaluation. Our medical director or PI will contact the patient within 24 hours after the referral to ensure that the patient has followed through with the referral. We also have referral sources in place to provide psychiatric treatment if necessary. This protocol has been used successfully in our previous work, including studies of patients with major depression.

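### For the same BDI-II item 9 response, the Safety Monitoring section gives a longer response time and names fewer visits than the Risk/Benefit Assessment section, and neither says which governs

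*Combined protocol and SAP*

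**What the plan says.** All of this is in the combined protocol and SAP.

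- **Risk/Benefit Assessment.** The rule opens "Any enrolled patient who becomes actively suicidal (i.e., who scores" above 1 and continues "on item 9 of BDI-II) will be immediately evaluated by our study psychologist for suicidal plans and intent". The next step is conditional: "If a patient is considered acutely suicidal, he or she will be dropped from further participation", and such a patient "will be referred for either urgent evaluation by a psychiatrist or prompt ED evaluation". The section also provides for psychiatric referral of any participant found to be actively suicidal during the trial. It bars enrolment of people with current active suicidal ideation.
- **Safety Monitoring.** One sentence says that acutely suicidal patients are evaluated by the study psychologist, referred or admitted as appropriate, and removed from the study. The following sentence makes this specific. It places in brackets, beside the term *acutely suicidal*, an item 9 response of 2 or 3 "at the end of the 6-week run-in or after the 6-week CBT-I treatment program". For these participants it says "they will be evaluated by our study psychologist within 24 hours and will be referred for treatment as needed".
- **Section C.6 (Quality of Life Assessments).** The BDI-II belongs to the set introduced by "The following assessments will be made at baseline, post-6-week run-in, post-CBT-I intervention, and at 6-month follow-up".

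**The concern.** Both sections are triggered by the same answer on the same item and call for the same action by the same person, yet they differ on how soon and at which visits. They also use different labels: the response is *actively* suicidal in one section and *acutely* suicidal in the other. The second label matters because both sections attach removal from the study to being acutely suicidal.

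What is at stake is mainly participant safety and protocol compliance. A coordinator would naturally look under Safety Monitoring, and could follow it to the letter while departing from the Risk/Benefit Assessment section. Two coordinators could handle the same answer differently, each with text to support the choice. A secondary matter is follow-up: whoever is removed stops contributing post-treatment or 6-month data, so the plan should be clear about what triggers removal.

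**Working it through.** No sample size, power or error rate is involved, so the check is a comparison of the two rules with each other and with the BDI-II schedule.

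| Element | Risk/Benefit Assessment | Safety Monitoring | Same? |
|---|---|---|---|
| Item 9 trigger | above 1 | 2 or 3 | yes |
| Label for that response | actively suicidal | acutely suicidal | no |
| Time to psychologist's evaluation | immediate | up to 24 hours | no |
| Visits | any enrolled patient, no visit limit | end of run-in; after CBT-I | no |
| Who is removed | a patient considered acutely suicidal | acutely suicidal patients, with the score in brackets beside that term | unclear |

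1. **Trigger.** Assume whole-number scoring with a maximum of 3, which fits Safety Monitoring listing 2 and 3 as the positive responses. Above 1 then means 2 or 3, so the two rules apply to the same answers.

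2. **Response time.** The actor and the action are the same and the deadline differs. The Risk/Benefit Assessment section does contain a 24-hour limit, but it applies to a later step: contact by the medical director or PI after a referral has been made. It does not explain the 24 hours in Safety Monitoring.

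3. **Visits.** Section C.6 gives 4 scheduled administrations. Safety Monitoring names 2, so 4 − 2 = 2 are unnamed: baseline and 6 months.
   - At 6 months the Risk/Benefit Assessment rule applies, because it covers any enrolled patient without a visit limit.
   - At baseline, either the participant is already enrolled and the same rule applies, or the participant is not yet enrolled and the entry restrictions apply. Those are the bar on current active ideation and the exclusion for prominent suicidal ideation under Selection of Subjects.
   - Across the two sections together, therefore, no administration after enrolment is without a rule. The narrower coverage belongs to Safety Monitoring alone.

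4. **Removal.** In the Risk/Benefit Assessment section the score leads to evaluation, and removal follows only if the patient is then considered acutely suicidal. Safety Monitoring supports two readings:
   - The bracket defines *acutely suicidal* for the preceding sentence, so a response of 2 or 3 is enough for removal. The linking word at the start of the second sentence favours this.
   - The second sentence is complete in itself. It prescribes evaluation and then referral according to need, which leaves removal to judgement, as in the other section.
   
   The text does not settle which is meant.

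5. **Precedence.** Neither section refers to the other or says which prevails.

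**The case against.** The strongest reply is that the two rules can be met together. An immediate evaluation is also an evaluation within 24 hours, so staff who follow the Risk/Benefit Assessment section breach nothing in Safety Monitoring, and the 24 hours can be read as an outer limit. This is right as far as it goes: the instructions are not mutually exclusive on timing. It does not work in reverse, however. Staff who act on Safety Monitoring alone may not satisfy the other section, and nothing tells them to look there.

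It can also be said that the reference to a time after the CBT-I programme may include the 6-month visit, since Safety Monitoring places follow-up 6 months after the intervention. That reading is possible. Section C.6, however, lists the post-CBT-I and 6-month assessments separately, so the more natural reading is the narrower one.

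Three stronger conclusions are tempting and are not supported:

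- **That a positive item 9 response at 6 months has no rule.** The Risk/Benefit Assessment section covers it.
- **That the sections flatly contradict each other on who leaves the study.** This requires carrying removal from one Safety Monitoring sentence into the bracket of the next, and the item 9 sentence itself mentions only evaluation and referral. It is an ambiguity, made worse by the two labels, and not a demonstrated contradiction.
- **That removals would bias the results by taking out poor sleep responders.** Nothing in the documents links item 9 responses to the response to CBT-I.

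**Conclusion.** The inconsistency is real and modest. For identical item 9 responses, Safety Monitoring allows up to 24 hours where the Risk/Benefit Assessment section requires immediate evaluation, and it names 2 of the 4 scheduled BDI-II administrations where the other section has no visit limit. The labels differ, precedence is not stated, and it is uncertain whether the score alone ends participation under Safety Monitoring.

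The time and visit differences rest on explicit text, apart from the scoring assumption in step 1 and the natural reading of the visit wording. The point about removal is an ambiguity only. The documents give no expected frequency of such responses. Because the entry criteria screen out active or prominent suicidal ideation, the number affected is likely to be small, and no effect on any estimate is shown. The text should still be corrected, because it governs participant safety and the correction is cheap. Nothing here implies that either section's clinical content is the right one.

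**What to change.** Reconcile the item 9 text in Risk/Benefit Assessment and Safety Monitoring into a single rule, stated once and cross-referenced from the other section. It should give:

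- one trigger and one label for the response;
- one response time for the psychologist's evaluation;
- an explicit list of the visits covered, including whether the baseline and 6-month BDI-II are within it;
- a statement of whether the item 9 score or the psychologist's judgement ends participation.

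The study's clinical leads should decide what each of these says. The cost is a change of protocol wording, an IRB text amendment and a memo to staff. No assessment, sample size or analysis changes.
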